### **5.6 Subject Follow-Up**

While on the first twelve weeks of therapy, participants will be undergo clinical (including cGVHD) and immunologic evaluations every 3 weeks. cGVHD severity/response will be assessed using the NIH scoring criteria (see Appendix).

Toxicity assessments will be performed using the CTEP Version 4.03 of the NCI Common Terminology Criteria for Adverse Events (CTCAE) which is identified and located on the CTEP website at: [http://ctep.cancer.gov/protocolDevelopment/electronic\\_applications/ctc.htm](http://ctep.cancer.gov/protocolDevelopment/electronic_applications/ctc.htm).

If possible, adverse effects should be managed symptomatically. In the case of toxicity, appropriate medical treatment should be used (including anti-emetics, anti-diarrheals, etc.). All CTCAE grade 3 and higher adverse events experienced by participants will be collected from the time of the first dose of study treatment, through the study and until the final study visit.

Participants removed from the study for unacceptable adverse events will be followed until resolution or stabilization of the adverse event. Follow-up for participants benefiting on extended-duration therapy will continue on monthly basis in the GVHD clinic.

## 5.7 Supportive Care, Other Concomitant Therapy, Prohibited Medications

Antiviral, antifungal and antibacterial prophylaxis and monitoring should follow institutional practice for routine cGVHD management guidelines. These typically include: daily acyclovir (or equivalent) for HSV prophylaxis, bactrim (or equivalent) for PCP prophylaxis, IV gammaglobulin for hypogammaglobulinemia, and optional azole use for fungal prophylaxis in higher risk patients; as well as monitoring of CMV viral load, beta-glucan and galactomannan levels.

## 5.8 Additional Studies:

Baseline evaluations, tests or exams are valid 3 weeks prior to the start of treatment.

At baseline, weeks 3, 7, 9, 12 and 16, an additional 30ml of whole blood will be collected in EDTA tube (lavender top) for flow cytometry of immune cell subsets and 5 ml in serum separator tube (yellow top) for cytokine analysis.

### 5.8.1 Immune Cell Subsets:

- Effector memory cells ( CD 45RA-CCR7-/CD62-) 
- Th17 cells 
- Tregs ( CD4+CD25+CD127-) 
- TRECS (T cell receptor excision circles) 
- CD3+ Cells ( T con) 
- CD 19+( B cell marker) 
- CD3-CD16+CD56+( NK cells) 
- FoxP3 gene methylation status

### 5.8.2 Inflammatory Markers:

- IFN- $\gamma$ , TNF  $\alpha$  
- IL-2, IL-4, IL-6, IL-8 
- IFN- $\gamma$ , TNF  $\alpha$  
- BAFF 
- IL-2 receptor  $\alpha$  (IL2R $\alpha$ ) and hepatocyte growth factor (HGF) for systemic GVHD 
- Elafin for skin GVHD 
- Regenerating islet-derived 3 $\alpha$  (REG3 $\alpha$ ) for gastrointestinal GVHD 
- Suppression of tumorigenicity 2 (ST2) for steroid-refractoriness 
- CXCL9 
- Micro RNA analysis 
- Plasma banking to be done for microRNA analysis for cGVHD .
- Skin biopsy specimens will be taken at beginning and end of therapy as clinically appropriate.

## 5.9 Definition of Dose-Limiting Toxicity (DLT)

Not applicable. See section 6.0 for dose and schedule modifications for toxicity.

## 6.0 Dose Delays/Modifications for Adverse Events

---

Dose delays and modifications will be made using the following recommendations as described below. Toxicity assessments will be done using the CTEP Version 4.03 of the NCI Common Terminology Criteria for Adverse Events (CTCAE) which is identified and located on the CTEP website at: [http://ctep.cancer.gov/protocolDevelopment/electronic\\_applications/ctc.htm](http://ctep.cancer.gov/protocolDevelopment/electronic_applications/ctc.htm).

### 6.1 IL-2 Therapy

The dose modifications as described below are required for patients in the first 12 weeks of study and recommended but not mandatory for participants proceeding on extended duration therapy at the end of the 12-week study.

- Unexpected CTC Grade 3 toxicity: IL-2 will be withheld for unexpected non-hematologic toxicities that are grade 3. Expected IL-2 toxicities are listed in Section 8.1.3. If the toxicity resolves to grade 1 or below within 2 weeks, IL-2 can be restarted at a 50% reduced dose that will not be re-escalated. If the toxicity does not resolve in 2 weeks to grade 1 or below, or recurs to grade 3 or above after restarting IL-2, IL-2 will be discontinued.
- Expected non-hematologic toxicity: IL-2 can be withheld and/or restarted at a 50% reduced dose for less than grade 3 toxicity (e.g. local site reactions, persistent constitutional symptoms) in the interest of patient tolerability and at the discretion of the treating physician.
- Severe (grade-4) hematologic toxicity: IL-2 will be withheld for severe declines in peripheral counts (ANC<500, Plts<10,000) not related to malignant disease relapse, infection or other etiologies. If counts improve (ANC>1000, Plts>20,000) within 2 weeks, IL-2 will be restarted at a 50% reduced dose and not re-escalated. If peripheral counts do not improve within 2 weeks, or drop again (ANC<500, Plts<10,000) after restarting IL-2, it will be discontinued. Use of myeloid growth factors and transfusion of platelet and PRBC's will be per standard institutional guidelines and is allowed while patients are on trial.
- Infection: Of note, infection during IL-2 treatment is not considered IL-2 related, since both cGVHD and the concurrent use of immune suppression medications are known risk factors for infection. Infection is therefore considered an expected complication of cGVHD. However, patients who develop a CTC grade 3 or higher infection prior to week 12 of IL-2 therapy will have IL-2 withheld. They can be considered for restarting IL-2 at their prior dose after control of infection, at the discretion of the treating physician.
- Treatment Interruption: Within the first 12 weeks of IL-2 therapy, a  $\geq 6$ -week interruption will result in the participant being considered unevaluable for response (or lack thereof), unless objective improvement of cGVHD is documented with a shorter course of IL-2.

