### 6.2 Extracorporeal photopheresis:

The incidence of ECP reported side effects is extremely low at less than 0.003% especially in cGVHD patient population. The procedural risks with new third generation ECP devices is even smaller. Many of the complications attributable to ECP are related to vascular access. It would be preferable to use peripheral veins, but patients with cGVHD frequently have poor veins, and alternative access must therefore be used. When central venous catheters are used, complications such as infection, clotting in the catheters, deep venous thrombosis, and vessel stenosis can occur.

For this study, modifications of ECP therapy as described below are required for patients in the first 12 weeks of study. Infection: Of note, infection during ECP+ IL-2 treatment is not considered intervention-related, since both cGVHD and the concurrent use of immune suppression medications are known risk

factors for infection. Infection is therefore considered an expected complication of cGVHD. However, patients who develop a CTC grade 3 or higher infection prior to week 12 of ECP+ IL-2 therapy will have therapy withheld during active infection. They can be considered for restarting ECP after control of infection, at the discretion of the treating physician. CVP line infection and bacteremia/sepsis requiring line removal will result in temporary stoppage of ECP therapy.

- Severe (grade-4) hematologic toxicity: ECP+IL-2 will be withheld for severe declines in peripheral counts (ANC<500, Plts<10,000) not related to malignant disease relapse, infection or other etiologies. If counts improve (ANC>1000, Plts>20,000) within 2 weeks, ECP will be restarted per schedule. If peripheral counts do not improve within 2 weeks, or drop again (ANC<500, Plts<10,000) after restarting ECP + IL-2, it will be discontinued. Use of myeloid growth factors and transfusion of platelet and PRBC's will be per standard institutional guidelines and is allowed while patients are on trial.

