- Central Line associated venous thrombosis: If adequate flow volumes can be generated with clot in situ and patient has platelet counts >50,000/mm^3, patients will receive systemic anticoagulation with warfarin, enoxaparin or similar anticoagulant and ECP therapy will be continued per schedule. If, however, platelet counts are less than 50,000/mm^3, precluding anticoagulation therapy, the central line will be removed and therapeutic intervention stopped. ECP will be continued if peripheral access is available.
- Unexpected CTC Grade 3 toxicity: ECP+IL-2 will be withheld for unexpected non-hematologic toxicities that are grade 3. Expected ECP toxicities are listed in Section 8.1.4. If the toxicity resolves to grade 1 or below within 2 weeks, ECP+IL-2 can be restarted. If the toxicity does not resolve in 2 weeks to grade 1 or below, or recurs to grade 3 or above after restarting ECP+IL-2 will be discontinued.

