#### 8.1.4 Pharmacology – Handling, Storage, Dispensing and Disposal

##### 8.1.4.1 *Form:*

Recombinant human IL-2 (Proleukin®) is supplied as a sterile, white to off-white, lyophilized cake in single-use vials containing 22 MIU of aldesleukin intended for intravenous (IV) or subcutaneous (SC) administration. Store vials of lyophilized IL-2 in a refrigerator at 2-8°C (36-46°F). Do not use beyond the expiration date printed on the label.

For the 22 million international unit (MIU) vial, when reconstituted with 1.2 mL Sterile Water for Injection (SWFI), each mL contains 18 MIU (1.1mg) IL-2, 50 mg mannitol and ~180 mcg sodium dodecyl sulphate, buffered with ~170 mcg sodium phosphate monobasic and 890 mcg sodium phosphate dibasic to a pH of 7.5 (range: 7.2-7.8)

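### Section 6.1 gives no instruction for a first grade 3 thrombotic microangiopathy, and Section 6.2 fills the gap only on one reading of a wrong cross-reference

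*Combined protocol and SAP*

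**What the plan says.** Section 6.1 sets IL-2 dose rules that are required in the first 12 weeks.

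- **Unexpected grade 3:** "IL-2 will be withheld for unexpected non-hematologic toxicities that are grade 3. Expected IL-2 toxicities are listed in Section 8.1.3". If the event settles to grade 1 or below within 2 weeks, "IL-2 can be restarted at a 50% reduced dose that will not be re-escalated".
- **Expected non-hematologic toxicity:** "IL-2 can be withheld and/or restarted at a 50% reduced dose for less than grade 3 toxicity", at the treating physician's discretion. Nothing is said for expected events at grade 3.
- **Hematologic toxicity:** the hold applies at grade 4 counts only (ANC below 500 or platelets below 10,000).
- **Infection:** IL-2 is held at grade 3 or higher, but infection is declared not IL-2 related.

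Section 8.1.3 says that its list decides whether doses are delayed or modified. It lists TMA as expected in 7% of patients, describes the two phase I cases (one needed long-term hemodialysis), and gives no hold, dose or stopping instruction.

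Section 6.2 says that "modifications of ECP therapy as described below are required for patients in the first 12 weeks of study". Its grade 3 rule reads: "ECP+IL-2 will be withheld for unexpected non-hematologic toxicities that are grade 3. Expected ECP toxicities are listed in Section 8.1.4". Section 8.1.4 is headed "Handling, Storage, Dispensing and Disposal" and contains no toxicity list; the ECP toxicities are in 8.2.1, which does not name TMA. On restart, 6.2 says: "If the toxicity resolves to grade 1 or below within 2 weeks, ECP+IL-2 can be restarted".

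Section 5.5 removes patients for any grade 4 non-hematologic event and for a recurrent or non-resolving grade 3 event. Section 5.2.4 withholds therapy for intensive-care admission and for respiratory or hemodynamic compromise.

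**The concern.** Within 6.1, a grade 3 event that nobody foresaw triggers a mandatory hold, while a foreseen event that can cost a patient renal function does not. The protocol recognizes the risk at entry, because a history of TMA, HUS or TTP is an exclusion, but does not carry it into the dosing rules. IL-2 is normally self-injected at home from a supply of up to 2 weeks, so the written rule has to be clear to whoever is called first.

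Section 6.2 does not settle the matter. Whether it requires a hold for TMA depends on which list defines an expected event, and its pointer leads to a section with no such list. This is a question of patient safety, and it does not affect the two-stage design or its error rates.

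**Working it through.** **1. The plan's own TMA figure.** Sections 2.4.1.2 and 8.1.2 report 2 TMA cases in phase I and 28 patients evaluable for toxicity. 2/28 = 7.1%, which agrees with the 7% in 8.1.3. This is a rate for any grade.

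**2. Is grade 3 TMA expected?** The definition of an unexpected event in Section 7 (Adverse Event Name and Severity) turns on whether the event is listed, at the severity observed, and is consistent with the protocol's risk information. Section 8.1.3 lists TMA, calls the cases serious, and reports dialysis. Grade 3 therefore lies within the listed severity, and the 6.1 hold for unexpected events does not apply.

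**3. What each section requires for a first grade 3 TMA.** No section classes TMA as hematologic or non-hematologic. Section 8.1.3 lists it apart from its hematologic item, but that does not decide the class.

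| Reading | 6.1 | 6.2 |
|---|---|---|
| Non-hematologic, expectedness judged by the ECP list (8.1.4 as written or 8.2.1 as presumably meant) | Silent | Hold ECP and IL-2 |
| Non-hematologic, expectedness judged by the Section 7 definition | Silent | No hold |
| Hematologic | Hold only at the grade 4 count limits | Grade 3 hold does not apply; count limits only |

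**4. Other rules.** Section 5.5 does not act on a first grade 3 event at onset. It would remove a patient with grade 4 TMA only if TMA is classed as non-hematologic, so the hematologic reading widens the gap. Section 5.2.4 may catch some severe cases, but it is not a TMA rule.

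**5. How often.** Section 2.4.1.2 gives both TTP/HUS cases as grade IV and names no TMA among the grade III events. Taking that as 0 of 28 at grade 3, the exact 95% upper limit is 1 − 0.025^(1/28) = 12.3%, so the interval is 0% to 12.3%. In 24 patients this is 0 to 24 × 0.123 = 3.0 cases. The phase I list may not be exhaustive. It also pools three dose levels over 8 weeks, against 12 weeks at one dose here. The documents do not fix the frequency.

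**6. Restart after an unexpected grade 3 event (not TMA).** Both grade 3 bullets apply. Section 6.1 sets IL-2 at 50% of the prior dose without re-escalation, while 6.2 lets both therapies restart and states no IL-2 dose.

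**The case against.** The strongest reply is that little is left uncovered. Classed as non-hematologic, both phase I cases would have led to removal under 5.5 because they were grade IV. Recurrent or non-resolving grade 3 events are also covered, and so are intensive care and hemodynamic compromise. Silence in 6.1 combined with a hold in 6.2 gives a hold, and clinicians would probably stop IL-2 anyway. TMA was judged only possibly related to IL-2, and both patients were taking drugs known to cause it. All of this limits the gap to a first grade 3 TMA, but does not close it, since the 6.2 hold exists on only one of the three readings above.

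A reader might infer more than the text supports:

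- **That the protocol directs IL-2 to continue, or leaves the hold to discretion.** It does neither. The discretionary bullet covers only events below grade 3; at grade 3 the section is silent.
- **That TMA is the one listed category with no grade 3 action.** The hematologic count rule starts at grade 4, so that contrast fails. What distinguishes TMA is a known serious outcome with no management instruction at all.
- **That 6.1 and 6.2 give TMA restart doses differing twofold.** The 50% restart belongs to the bullet for unexpected events, which does not reach TMA. Even for unexpected events 6.2 is silent on the IL-2 dose, so 6.1 can govern; the fault is ambiguity, not contradiction.
- **That the 7% rate (24 × 0.07 = 1.7 cases) measures the gap.** That rate covers all grades, and both cases behind it were grade IV.

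**Conclusion.** The point stands in a narrow form and should be fixed. For a first grade 3 TMA, 6.1 is silent and 6.2 requires a hold only if expectedness is judged by the ECP list that it mislocates. The frequency is unknown (0 listed among 28, exact 95% CI 0% to 12.3%), so the case rests on the seriousness of the event and the low cost of the change. It assumes that TMA counts as expected because 8.1.3 lists it. It does not depend on how TMA is classed: a hematologic classification would make the gap wider. The missing IL-2 restart dose in 6.2 is a separate, smaller ambiguity about unexpected grade 3 events.

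**What to change.** **In 6.1,** add a separate TMA/HUS/TTP bullet. IL-2 is held as soon as TMA is suspected, whether the event is classed as hematologic or non-hematologic, and may restart if TMA is ruled out. The half-dose restart should not carry over automatically to confirmed TMA, so simply extending the existing grade 3 bullet would be the wrong edit. The investigators should state the rule for confirmed cases; permanent discontinuation would be consistent with the entry exclusion, though the documents do not settle it. The present rules for induration, fatigue and infection can stay.

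**In 6.2,** change the pointer from 8.1.4 to 8.2.1, state which list (8.1.3, 8.2.1 or both) decides expectedness for the combination, and state that any IL-2 restart follows 6.1.

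**Cost:** one bullet, one cross-reference and two sentences. A few more IL-2 interruptions will follow, some for suspected TMA later ruled out. Under 6.1 a gap of 6 weeks or more carries a penalty, since such an "interruption will result in the participant being considered unevaluable for response (or lack thereof"), unless objective improvement is documented with a shorter course. Prompt work-up of suspected cases would keep most holds well short of that.

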### 5.2.4 Documentation of compliance to therapy

Each participant will be given explicit instructions for taking IL-2 subcutaneous injections at home. Compliance to IL-2 home therapy will be closely monitored while they are on protocol therapy and patient will be given detailed instructions by the physician and research nurse in terms of administration of IL-2 subcutaneously and anticipated side effects. All enrolled patients will be given a drug diary (provided by the research nurse) at enrollment where they will document daily drug use and any missed doses and reasons thereof. The diary will be returned to the Research Nurse every 2 weeks while on protocol therapy and a new one will be issued at the same time.. IL-2 typically is supplied in  $22 \times 10^6$  units multidose vials and these will be individually dispensed in single dose syringes to enrolled patients every 2 weeks for home administration.

DO NOT ADMINISTER IL-2 AS INTRAVENOUS PUSH OR BOLUS.

Pre-medications are not required prior to the first dose or later doses.

All treatment including IL-2 administration and ECP procedures will be conducted in the outpatient setting, unless patient is hospitalized for some other medical condition unrelated to underlying hematologic disease or adverse effects of therapy (e.g. therapy will continue while inpatient for pain control, failure to thrive etc.). ICU admission, respiratory and hemodynamic compromise will be grounds for withholding therapy. See section 6.0 for dose modification and stoppage rules.

Prednisone (or equivalent steroid) will be continued concomitantly with IL-2 without dose modification. Taper of prednisone, or any other immune suppression medications, will not be permitted during the initial 6 weeks of the study, but can be reduced thereafter in responders at the discretion of the treating physician.

Of note, clinically stable cGVHD during taper of other immune suppression medications will be considered evidence of IL-2 efficacy; and progression of cGVHD during taper of other immunosuppressive therapy will not be considered evidence of IL-2 toxicity or lack of efficacy.

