### 8.1.3 Expected Toxicities with IL-2

A list of the adverse events and potential risks associated with the agents administered in this study appear below and will determine whether dose delays and modifications will be made or whether the event requires expedited reporting in addition to routine reporting.

*Local Reactions (expected in 10% patients):* Patients receiving daily SC low-dose IL-2 have been reported to develop injection site reactions, typically focal erythema that resolved in a few days; and induration that resolved after 2-3 weeks. Dose interruptions may occasionally be required in patients with more marked induration (CTCAE 4.0; Grade 3). Lengthy dose interruptions may result in patients being unevaluable for response (Section 6.1)

*Constitutional symptoms (expected in 5% patients):* In the allo-HCT setting, some patients on low-dose IL-2 developed fever, nausea and arthralgia within 72 hours of starting IL-2. Interruption of therapy for 3 days is recommended if symptoms reported are severe and affecting ADL's i.e. Fatigue  $\geq$  Grade 3 per CTCAE 4.0 criteria. If symptoms of fatigue resolve in 72 hours; IL-2 may be restarted at 50% of prior dose. If however symptoms of fatigue persist and patient is unwilling to continue therapy on protocol, they will be removed from study. Secondary/reversible causes of fatigue, such as sepsis, hypotension, hypothyroidism will be ruled out prior to attributing this to IL-2.

*Thyroid dysfunction (expected in 5% patients):* Thyroid function test abnormalities were noted in some allo-HCT patients on low-dose IL-2. Only one patient however developed clinical hypothyroidism necessitating therapy while on IL-2. After cessation of IL-2, thyroid function returned to normal. Hence, a thyroid panel (TSH, T4, free T4) levels will be checked at study entry and week 12 while on study. Patients with evidence for hypothyroidism will be worked up (antimicrosomal, antithyroglobulin antibodies) and given replacement thyroxine as clinically indicated.

*Hematologic (expected in 5% patients):* Early post-HSCT, low-dose IL-2 caused an initial decrease in the absolute lymphocyte count in patients after 1 week of therapy. Thereafter, with continued infusion, a steady increase in lymphocyte count occurred in all patients.

- Low dose IL-2 also caused an initial increase in eosinophil counts (peak at 3 weeks) followed by a gradual decline.

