### 13.1 Study Design, Sample Size, and Accrual Rate

This single center/single arm, phase II clinical trial is designed to evaluate the anti-cGVHD activity of extracorporeal photopheresis (ECP) when combined with low dose IL-2, in patients with steroid refractory cGVHD, as assessed by overall cGVHD response rate (CR+PR+SD). The primary endpoint overall response (CR+PR+SD) is based on the NIH cGVHD consensus criteria; calculated as the percent of evaluable patients that have confirmed CR/PR or SD

This study will implement a Simon, optimal, two-stage design to evaluate the anti-cGVHD activity of the ECP/IL-2 regimen. The trial is expected to enroll 24 patients e sample size is based on the desire to discriminate a promising response rate of 50% from a current response rate of 25%. The null hypothesis

that the true response rate is 25% will be tested against a one-sided alternative. In the first stage, 9 patients will be accrued. If there are 2 or fewer responses in these 9 patients, the study will be stopped. Otherwise, 15 additional patients will be accrued for a total of 24. The null hypothesis will be rejected if 10 or more responses are observed in 24 patients. This design yields a type I error rate of 0.05 and power of .80 when the true response rate is 50%. Currently, about 20-25 new patients are referred to ECP per year. We expect that 6 patients to be enrolled per year with the expected completion of accrual in 4 years.

**Evaluable for Response:** As part of the primary analysis, patients will be considered evaluable for response if they are eligible, have baseline disease assessments, and receive protocol treatment of any duration. All such patients will be evaluated for clinical response. Our primary outcome will be the clinical response rate measured in all patients who are enrolled and receive any amount of protocol therapy.

Patients who are consented for the study but withdraw for any reason (progression of GVHD, infectious complications, insurance denial etc) prior to initiation of protocol therapy will not be eligible for response evaluation.

**Evaluable for Toxicity:** Patients will be considered evaluable for toxicity if they receive any study drug.

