#### 13.2 Statistical Analysis Plan

Patient demographic and baseline characteristics, including age, gender, medical history, and prior cGVHD therapy, will be summarized using descriptive statistics. For continuous variables, descriptive

statistics (number [n], mean, standard deviation, standard error, median (range) will be provided. For categorical variables, patient counts and percentages will be provided.

The overall response rate (CR+PR) will be calculated as the percent of evaluable patients; exact 95% confidence intervals will be calculated for these estimates. Response rates will also be evaluated based on number and type of prior therapy(ies). Time to response, duration of response, and survival will be estimated using the product-limit method of Kaplan and Meier.

Observed toxicities will be summarized in terms of type (organ affected or laboratory determination), severity, time of onset, duration, probable association with the study treatment and reversibility or outcome. Baseline information (e.g. the extent/type of prior therapy) and demographic information will be presented as well to describe the patients treated in this study.

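### Section 6.1 removes patients with a long IL-2 interruption from response evaluation only if they did not improve, which contradicts the all-treated primary set in Section 13.1

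*Combined protocol and SAP*

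**What the plan says.** Section 13.1, under its evaluability heading, gives an all-treated rule for the primary analysis: "patients will be considered evaluable for response if they are eligible, have baseline disease assessments, and receive protocol treatment of any duration". It then repeats the point: "Our primary outcome will be the clinical response rate measured in all patients who are enrolled and receive any amount of protocol therapy". The only withdrawals it excludes are those before protocol therapy starts. The same section counts stable disease (SD) as a success, with the rate "calculated as the percent of evaluable patients that have confirmed CR/PR or SD". The null hypothesis is "rejected if 10 or more responses are observed in 24 patients", after a first stage of 9 patients that stops the trial at 2 or fewer responses.

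Section 6.1, in its treatment-interruption bullet, has a different rule. After an IL-2 interruption of at least six weeks within the first 12 weeks, the participant is "considered unevaluable for response (or lack thereof), unless objective improvement of cGVHD is documented with a shorter course of IL-2". Section 8.1.3 (local reactions) points back to this rule.

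Section 13.2 also uses evaluable patients as the denominator, without saying whose definition applies: "The overall response rate (CR+PR) will be calculated as the percent of evaluable patients".

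**The concern.** Take two patients with the same long interruption, one improved and one not. Under 6.1 the first is counted and the second is not. Membership of the denominator is then decided partly by the outcome being estimated. Under 13.1 both are counted. The two rules cannot both apply to the second patient.

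The 6.1 exception also does not match the endpoint. It keeps patients with objective improvement, but 13.1 treats SD as a success. An interrupted patient with SD is a success under 13.1 and absent under 6.1.

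The scope of 6.1 is unclear too. It does not say whether permanent discontinuation before week 6 counts as an interruption. If it does, early stoppers without improvement would also leave the denominator.

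At stake are the reported primary rate and, where successes include SD, the power of the test. With 24 patients and a cut-off of 10, one classification can decide the result, so the rule should be settled before outcomes are known.

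**Working it through.** **Inputs from Section 13.1.** Null rate 0.25, target rate 0.50, one-sided test. Stage 1 has 9 patients and stops at 2 or fewer responses. The total is 24, with rejection at 10 or more.

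**Inputs assumed.** q is the share of treated patients with an interruption of six weeks or more. The documents give none, so I use 2%, 5% and 10% (about 0.5, 1.2 and 2.4 of 24 patients), independent of response. f is the share of successes that are SD: 0, one half or 1.

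**Step 1: the plan's own design.** P(reject) = Σ over x = 3 to 9 of Bin(x; 9, p) × P(Bin(15, p) ≥ 10 − x). This gives 0.0485 at p = 0.25 and 0.8055 at p = 0.50, in agreement with the stated 0.05 and 0.80.

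**Step 2: expected rate in the 6.1 set when all successes are improvers (f = 0).** Interrupted non-improvers, a fraction q(1 − p), leave the denominator, so the rate becomes p / (1 − q(1 − p)). For example, 0.25 / (1 − 0.10 × 0.75) = 0.25 / 0.925 = 0.270.

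| True rate | q = 2% | q = 5% | q = 10% |
|---|---|---|---|
| 25% | 25.4% | 26.0% | 27.0% |
| 50% | 50.5% | 51.3% | 52.6% |

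**Step 3: the same rate when some successes are SD.** Interrupted SD patients leave both numerator and denominator, so the rate is p(1 − fq) / (1 − q(1 − p + fp)). At f = 0.5 and q = 10% this is 0.2375 / 0.9125 = 26.0% and 0.475 / 0.925 = 51.4%. At f = 1 it equals p, so there is no bias.

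**Step 4: the test with the fixed count and no replacement.** Only lost SD successes matter. The chance that an accrued patient counts as a success is p(1 − fq), which goes into the Step 1 formula.

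| f | Quantity | q = 2% | q = 5% | q = 10% |
|---|---|---|---|---|
| 0 | Type I error | 0.0485 | 0.0485 | 0.0485 |
| 0 | Power | 0.805 | 0.805 | 0.805 |
| 0.5 | Type I error | 0.046 | 0.041 | 0.035 |
| 0.5 | Power | 0.793 | 0.773 | 0.737 |
| 1 | Type I error | 0.043 | 0.035 | 0.025 |
| 1 | Power | 0.78 | 0.74 | 0.66 |

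**Step 5: if dropped patients were replaced.** The Step 2 rates would then go into the Step 1 formula. Type I error would be 0.061 at q = 5% and 0.077 at q = 10%. No section provides for replacement, so I do not rely on this case.

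**Step 6: illustration with exact 95% intervals.** Nine successes in 24 is 37.5% (18.8 to 59.4). Dropping one interrupted non-improver gives 9/23 = 39.1% (19.7 to 61.5). Dropping three gives 9/21 = 42.9% (21.8 to 66.0). Nine misses the cut-off of 10 in each case, so only the estimate moves.

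**The case against.** The best defence is that 13.1 already settles the matter. It is the statistical text, it refers explicitly to the primary analysis, and it states the all-treated rule twice. The 6.1 sentence sits among the dose-modification rules and does not mention the primary analysis. Section 8.1.3 only says that long interruptions may have this effect and refers back. I accept that 13.1 is the more natural governing text, that evaluable in 13.2 most naturally means the 13.1 definition, and that if 13.1 is followed 6.1 changes nothing. However, 6.1 is worded as an operative rule, another section cites it, and nothing subordinates it.

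The trigger may also be rare. Unresolved unexpected grade 3 and grade 4 hematologic toxicities lead to discontinuation after two weeks, and 6.1 uses the terms interruption and discontinuation separately. That is fair, and the rates above are assumptions. The phrase about a shorter course of IL-2 still leaves early stoppers ambiguous.

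The effects are modest and do not reach their maxima together. The bias is largest when no success is SD, where power is untouched. The power loss is largest when every success is SD, where the bias is zero. The shift in the estimate is also small beside a confidence interval about 40 points wide. All of this stands. It limits the weight of the point but does not reconcile the two rules.

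**Conclusion.** The concern holds. Sections 6.1 and 13.1 define incompatible denominators, and the 6.1 version depends on the outcome. If 6.1 were followed, and with 2% to 10% of patients interrupted independently of response, the reported rate would be inflated by at most about 2 to 3 percentage points at q = 10%, when all successes are improvers. If half the successes are SD, power would fall to between 0.793 and 0.737. Type I error would not exceed its design value of 0.0485, because the cut-off is a fixed count and no replacement is planned. Interruptions concentrated in patients who are doing badly would make the upward bias larger. The inconsistency is certain. Its practical size depends on an interruption rate that the documents do not give. It should be fixed, but it does not undermine the design.

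**What to change.** State in 6.1, 8.1.3 and 13.1 that the all-treated set of 13.1 governs the primary analysis and that interruption or discontinuation of IL-2 does not remove a patient from the denominator. State that an interrupted patient without a documented response, as the primary endpoint defines it, counts as a non-responder. In 13.2, tie evaluable patients to the 13.1 definition. Keep the 6.1 set as a labelled sensitivity analysis only.

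Two related clarifications can be made at the same time, although the conclusion does not rest on them. Section 5.2.4 says that "progression of cGVHD during taper of other immunosuppressive therapy will not be considered evidence of IL-2 toxicity or lack of efficacy", while the progression definition in 11.1.1 has no exception for taper. State that the 5.2.4 sentence concerns attribution to IL-2 and that progression meeting the NIH criteria during taper is still scored as progression. If SD remains a success, state how patients who start new immunosuppression for worsening disease before the response assessment are classified.

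The cost is wording in 5.2.4, 6.1, 8.1.3, 13.1 and 13.2. No new data are needed and no treatment rule changes. The reported response rate may be slightly lower than under 6.1.
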